
a: Includes height and weight. Height collected only during the screening window
 
b: Temperature, blood pressure, respiratory rate and pulse rate. Obtain twice on day of imaging: once prior to injection and once post-injection prior to discharge
 
c: Glucose, Na, K, Cl, Carbonate (CO₂), Mg, Ca, BUN, creatinine, AST, ALT, ALP, total protein, albumin, and total bilirubin
 
d: Frequency as per institutional standard of care; tumor burden assessment is obtained from surgical, pathology and/or imaging reports
 
e: As per institution's practice. If urine pregnancy test is inconclusive, a serum pregnancy test must be performed with results reviewed prior to study drug administration
 
f: Only if necessary for adverse event assessment; symptom directed exam is acceptable
 
g: IHC will be performed for FAP expression at a central lab on biopsy tissue; Histopathology for the detection of pancreatic cancer is performed locally
 
h: Passive follow-up only through chart review to collect information about post-surgical imaging, planned treatment, and outcomes for 14 days following surgery
 
i: AE assessments will be performed 24 hours post [⁶⁸Ga]FAPI-46 injection
 
j: Follow up visits may be performed through televisits. Patients may utilize institution approved local labs/mobile clinics for blood draws as part of follow up assessment. Subjects may enter surgery <24 hours post-injection if the time of Visit 2 follow-up assessment is 10 half-lives or more post [⁶⁸Ga]FAPI-46 injection
 
k: Labs obtained during screening period, within 72 hours of Day 1, can be used as pre-FAPI-46 injection Day1 lab data
					

Cohort 2: Participants who undergo NAT before being considered as surgical candidates by their doctor**Note:** days are counted as calendar days unless otherwise specified. The day before study day 1 is Day -1.

Study Procedure	Screen	Visit 1	Visit 2 ^j	Neo- adjuvant Treatment Period	Visit 3	Visit 4 ⁱ	Surgery	Surveillance Period (14 Days) ^h
	≤ 28 days of D1	Study day 1	+ 24 – 72h post-injection		≤ 21 days of surgery	+ 24 – 72h post- injection		
Informed consent	X							
Complete medical history, including surgical history	X							
Core biopsy obtained prior to NAT		X						
Standard of care imaging: CT, MR and/or [¹⁸ F]-FDG PET	X				X ^k			
Record concomitant medications	X	X	X	X	X	X		
Physical examination ^a	X		X ^f		X ^f	X ^f		
ECOG Performance Status	X	X						
Vital signs ^b	X	X			X	X		

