Within the reporting requirement under 21 CFR§312.32(c)(1)(i), FDA makes clear the meaning of reasonable possibility by providing the following examples of types of evidence that would suggest a causal relationship between the drug and the adverse event.

- A single occurrence of an event that is uncommon and known to be strongly associated with drug exposure (e.g., angioedema, hepatic injury, Stevens-Johnson Syndrome)
- One or more occurrences of an event that is not commonly associated with drug exposure, but is otherwise uncommon in the population exposed to the drug (e.g., tendon rupture)
- An aggregate analysis of specific events observed in a clinical trial (such as known consequences of the underlying disease or condition under investigation or other events that those events occur more frequently in the drug treatment group than in a concurrent or historical control group)

Although the sponsor is responsible for determining whether there is a reasonable possibility that the drug caused the adverse event, taking into consideration the investigator's assessment, the FDA requires the clinical investigator provide the sponsor with their assessment of causality for all serious adverse events.

- **Laboratory Abnormalities**

All abnormal laboratory results pre-categorized within the CTCAE v5 meeting grade 3 or 4 severity will be recorded and reported as AEs.

An abnormal laboratory result pre-categorized within the CTCAE v5 meeting grade 1 or 2 severity will be recorded and reported as an AE if the investigator deems the result clinically significant.

An abnormal laboratory result not pre-categorized within the CTCAE v5 (e.g., increased eosinophils, decreased creatinine) will not be captured as an adverse event unless deemed clinically significant by the investigator. The investigator must deem the result "mild," "moderate," "severe," or "life threatening," with the clinically significant notation.

- **Clinical Syndrome/Diagnosis vs. Symptomatic Components**

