9.3 Baseline Definition

Baseline for a given parameter is defined as the last non-missing evaluation before the first dose of [⁶⁸Ga]FAPI-46 for Cohort 1 and 2.

In addition, given NAT in Cohort 2 and [⁶⁸Ga]FAPI-46 are excreted from the body after 10 half-lives (\pm 10 hours), assessments after NAT and the last non-missing evaluation before the second dose of [⁶⁸Ga]FAPI-46 will be considered as post-NAT Baseline. Also, a pre- and post- NAT evaluation will be considered to evaluate the change in assessments before and after NAT and will be described in each relative section. Any assessment between the first dose of [⁶⁸Ga]FAPI-46 and NAT will be considered as post study treatment. Summaries will clearly indicate the difference between change from baseline (CFB) (if applicable) and change from pre-NAT.

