10.7.1 Adverse Events

The verbatim terms used in the eCRF to identify AEs will be coded using MedDRA Version 25.0. AE severity will be evaluated utilizing the CTCAE Version 5.0 ([Appendices](#)) toxicity grade as Grade 1, Grade 2, Grade 3, Grade 4, or Grade 5.

For the purposes of this study, the AE collection window is from the time of injection with [⁶⁸Ga]FAPI-46 through 24 hours postinjection. If the 24-hour window ends on a holiday or nonclinic day (or the patient cannot return to clinic due to unforeseen circumstances, such as weather), the window may be extended until 72 hours postinjection. TEAE summaries will present all AE recorded in the eCRF.

AE collection windows are tied to the number of [⁶⁸Ga]FAPI-46 injections. Cohort 1 will have 1 AE collection window whereas Cohort 2 will have 2 discrete AE collection windows. All collected AEs will be considered TEAE.

A TEAE overview table containing the frequency and percentage of patients as well as number of reported events in each of the following categories (summarized by cohort) will be presented:

- TEAEs
- Serious TEAEs
- TEAE by maximum toxicity grade (CTCAE Version 5.0)
- Study drug-related TEAEs
- Serious study drug-related TEAEs
- Fatal TEAEs

Additionally, the following will be summarized by cohort, SOC, and PT:

- TEAEs
- Serious TEAEs

- TEAEs by maximum toxicity grade (CTCAE Version 5.0)
- Study drug-related TEAEs
- Fatal TEAEs

Summaries of TEAEs by SOC and PT will be sorted alphabetically by SOC and by decreasing frequency of PT overall. If a patient has more than 1 TEAE at a given level (eg, SOC and/or PT), the patient will only be counted once within that level. When summarizing TEAEs by maximum CTCAE toxicity grade, at each level of summarization, patients who report 1 or more TEAEs within that level are only counted once at that level using the event of greatest CTCAE toxicity grade (in toxicity tables). Patients who have reported TEAEs that are missing CTCAE toxicity grade or relationship to study drug will not be summarized in the tables by toxicity grade or relatedness, however they will be included in the listings of AEs and tables not summarized by toxicity grade or relatedness. All tables will show the number and percent of patients with at least 1 TEAE (or SAE, per the criteria in the table).

The following listings will be provided:

- Listing of all TEAEs.
- Listing of patients with serious TEAEs
- Listing of patients with TEAEs leading to Death

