Appendix 2. Imputation of Partial Dates

Table 6. Imputation Rules for Partial Dates – Adverse Events

Parameter	Missing	Additional Condition	Imputation
Start Date	D only	M and Y are prior to first study drug dose	First day of indicated month
		M and Y is same as first study drug dose	Date of first study drug dose
		M and Y are after first study drug dose	First day of indicated month
	M and D	Y is prior to first study drug dose	01 Jan of indicated year
		Y is same as first study drug dose	Date of first study drug dose
		Y is after first study drug dose	01 Jan of indicated year
	M, D, and Y	-	assumed to be TEAE
End Date	D only	M and Y are prior to last study drug dose	Last day of indicated month
		M and Y is same as last study drug dose	Date of last observation
		M and Y are after last study drug dose	First day of indicated month
	M and D	Y is prior to last study drug dose	31 Dec of indicated year
		Y is same as last study drug dose	Date of last observation
		Y is after last study drug dose	01 Jan of indicated year
	M, D, and Y	-	TEAE is ongoing
	-	Estimated end date is before a complete or imputed AE start date	Last day of the month of AE start date

Abbreviations: D = day; M = month; Y = year; TEAE = treatment emergent adverse event

Note: The imputation of end date must be later than start date. In general, the minimum between AE end date and study drug date should be use for start date where applicable.

Table 7. Imputation Rules for Partial Dates – Prior and Concomitant Medications

Parameter	Missing	Additional Condition	Imputation
Start Date	D only	M and Y same as M and Y of first study drug dosing	Date of first study drug dose
		M and/or Y not the same as M and Y of first study drug dosing	First day of indicated month
	M and D	Y same as Y of first study drug dosing	Date of first study drug dose
		Y not the same as Y of first study drug dosing	01 Jan of indicated year
		Y same as Y of first drug dose and Y is equal to screening Y	Screening year
	M, D, and Y	none – date completely missing	Date of first study drug dose
End Date	D only	M and Y same as M and Y of last study drug dosing	Date of last study drug dose
		M and/or Y not the same as M and Y of last study drug dosing	Last day of indicated month
	M and D	Y same as Y of last study drug dosing	Date of last study drug dose
		Y not the same as Y of last study drug dosing	31 Dec of indicated year
	M, D, and Y	none – date completely missing	Date of last study drug dose

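### Every recorded AE counts as treatment-emergent, so a grade 3-4 laboratory value already present before injection and unchanged afterwards can enter the all-causality TEAE and maximum-grade tables

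*SAP*

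**What the plan says.** **TEAE rule.** SAP 10.7.1 says "TEAE summaries will present all AE recorded in the eCRF" and then "All collected AEs will be considered TEAE". It refers to protocol 7.2 for AE definitions, but that section does not define a TEAE, so these two sentences are the whole rule.

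**Laboratory AEs.** Protocol 7.2.3 says "All abnormal laboratory results pre-categorized within the CTCAE v5 meeting grade 3 or 4 severity will be recorded and reported as AEs". A lower-grade result "meeting grade 1 or 2 severity will be recorded and reported as an AE if the investigator deems the result clinically significant". The grade 3-4 rule has no such judgement and makes no reference to an earlier value.

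**Collection window.** Protocol 7.2.1 and SAP 10.7.1 run AE collection from injection to 24 hours, extendable to 72 hours in stated circumstances. Cohort 1 has one window and Cohort 2 has two. Outside the window, only AEs suspected to be related are to be reported.

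**Baselines.** SAP 9.3 defines a baseline before the first dose. For Cohort 2 it also names "assessments after NAT and the last non-missing evaluation before the second dose of" study drug as the post-NAT baseline. The TEAE rule uses neither.

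**Dates.** SAP Appendix 2, Table 6, has a start-date row for the case "M and Y are prior to first study drug dose". It calls an event a TEAE by assumption only when the start date is completely missing.

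**The concern.** Treatment-emergent normally means new or worse after exposure. Here the only filter is whether an AE was recorded. For most clinical events, the opening of the window at injection does the work of an onset rule. It does not do so for a laboratory abnormality that predates the injection and is measured again afterwards, because the protocol makes the second measurement an AE in its own right.

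Further characterising safety is a secondary objective, and its endpoint is the incidence and severity of all TEAEs, not only related ones. With a single arm, no control group shows how much of the count is background. A table of TEAEs by maximum grade that contains unchanged grade 3-4 values would describe the patients' prior condition as if it had followed the tracer.

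**Working it through.** The plan gives no figure on this point. Its power figure (92.7% for sensitivity with 60 patients) does not depend on the TEAE rule. The check is therefore a trace through the text, followed by an illustration of size.

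**Trace for one Cohort 2 patient**

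1. Chemistry and CBC are scheduled at Visit 3, the day of the second injection, and again at Visit 4 (protocol 1.3). Protocol 7.1.9 requires the CBC result before injection.
2. Suppose neutrophils are grade 3 after NAT at Visit 3, before injection, and still grade 3 at Visit 4.
3. The Visit 4 result falls under the rule that grade 3-4 results "meeting grade 3 or 4 severity will be recorded and reported as AEs".
4. Under SAP 10.7.1 the AE becomes a TEAE and is counted at grade 3, although nothing changed across the injection.
5. Compared with the post-NAT baseline of SAP 9.3, the change in grade is 0, but no rule makes that comparison.

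The same steps apply in either cohort to a value at grade 3-4 at both Visit 1 and Visit 2. Section 10.7.1 breaks the TEAE tables down by cohort, SOC and PT, not by injection, so Cohort 2's post-NAT window is not set apart there.

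**Internal consistency.** Table 6 imputes start dates before the first dose and reserves the TEAE assumption for fully missing dates. That matters only if TEAE status depends on dates. Under SAP 10.7.1 it does not.

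**Size (illustration only).** Let b be the probability, per window, that a grade 3-4 value present before injection persists at the post-injection draw, with no drug effect. The documents give neither b nor the cohort split. Both are assumed.

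- One window per patient: expected patients = 60 × b; chance of at least one = 1 − (1 − b)^60.
- 30 patients with two independent windows: expected patients = 30b + 30[1 − (1 − b)²].

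| b | One window: expected of 60 | Chance of at least one | 30 patients with two windows: expected of 60 |
|---|---|---|---|
| 2% | 1.2 | 70% | 1.8 |
| 5% | 3.0 | 95% | 4.4 |
| 10% | 6.0 | 99.8% | 8.7 |
| 30% | 18.0 | >99.9% | 24.3 |

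If only the post-NAT window of an assumed 30 Cohort 2 patients contributed, 5% would give 30 × 0.05 = 1.5 patients. Under a rule requiring new onset or a higher grade, each expected count would be 0, apart from cases that cannot be resolved.

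**Surgery.** Footnote j of the Cohort 1 schedule says "Subjects may enter surgery <24 hours post-injection if the time of Visit 2 follow-up assessment is 10 half-lives or more post" injection. With the 68-minute half-life in protocol 4.3.5, ten half-lives are 680 min = 11.33 h. At most 24 − 11.33 = 12.67 h of the 24-hour window could then fall after surgery begins.

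**The case against.** The strongest defence is that the collection window already acts as an onset rule. It opens at injection and closes at 24 to 72 hours, and outside it only suspected-related events are reported. Baseline signs and symptoms are recorded at Visits 1 and 3. Toxicity arising during NAT is therefore not collected as such. This stands for most clinical events and confines the problem mainly to laboratory values.

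Second, protocol 7.2.3 lets the investigator report an overarching diagnosis instead of the laboratory abnormality. That changes the term recorded, but the diagnosis is still an AE and so still a TEAE.

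Third, relatedness to drug and to the PET procedure is assessed, drug-related TEAEs are tabulated, and SAP 10.7.2 plans change-from-baseline and shift tables. These help a reader. However, the safety endpoint is all-causality, and the shift tables use low, normal and high rather than CTCAE grade. They neither remove the event nor show that its grade was unchanged.

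Fourth, counting everything is conservative: it over-reports rather than hides. That is fair and is why this is not a safety-critical fault, but the label treatment-emergent would still be wrong for these events.

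Fifth, Table 6's pre-dose rows may be generic and largely unused. They show that the SAP is inconsistent, not that many events are affected.

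**Conclusion.** The rule is wrong as written and should be changed. Applied literally, it classifies an unchanged grade 3-4 laboratory value as treatment-emergent. The effect falls on the all-causality TEAE and maximum-grade tables; the primary endpoint and the power are untouched. The mechanism rests on the text alone. Its size (3 of 60 at an assumed 5%; about 1 to 18 for 2% to 30%, one window per patient) rests wholly on assumed rates.

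A reader might infer more, but the documents do not support these readings:

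- **Serious and fatal tables.** Seriousness in protocol 7.2.2 depends on outcome or medical judgement. An unchanged laboratory grade does not by itself make an event serious or fatal.
- **Surgery generally contaminating the profile.** Footnote j applies to Cohort 1 and is conditional on the Visit 2 assessment. The schedule marks no AE assessment at surgery. Operative events could enter if sites record them, and 12.67 h is a ceiling, not an estimate.
- **Biliary disease as a source.** The chemistry panel invites the thought, but the documents do not name it.
- **A contrast with the more than 200 earlier scans without reported AEs in protocol 4.4.** That is a personal communication, per scan, with no stated collection method. It is not like-for-like with a per-patient laboratory rate.

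**What to change.** Replace the TEAE sentence in SAP 10.7.1 with a definition along these lines:

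- A TEAE is an AE with onset, or an increase in CTCAE grade, after a [68Ga]FAPI-46 injection relative to the last evaluation before that injection: the SAP 9.3 baseline for injection 1 and the post-NAT baseline for injection 2. For laboratory AEs, compare with the pre-injection grade, not only the recorded onset date.
- Any AE suspected to be related to study drug remains a TEAE.
- Cases that cannot be resolved (same-day onset, partial date, missing pre-injection value) default to TEAE.
- All other recorded AEs are listed and counted separately.

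Grade the pre-injection laboratory values by CTCAE and align Table 6 with the definition. Flag any recorded AE with onset on or after the day of surgery, so that its contribution can be seen.

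The cost is one derived flag, the grading of baseline laboratory values and one extra table. The protocol already schedules the laboratory draws needed. The limitation is that protocol 7.2.4 requires the date of onset but not the time, so some injection-day events will stay TEAEs by default. That errs on the conservative side.

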7.2.2. Definitions

This study defines terms as per the U.S. federal code at 21CFR§312.32:

- **Adverse event**

Any untoward medical occurrence associated with the use of a drug in humans, whether or not considered drug related.

- **Life-threatening adverse event or life-threatening suspected adverse reaction**

An adverse event or suspected adverse reaction is considered "life-threatening" if, in the view of either the investigator or sponsor, its occurrence places the patient or subject at immediate risk of death. It does not include an adverse event or suspected adverse reaction that, had it occurred in a more severe form, might have caused death.

- **Serious adverse event or serious suspected adverse reaction**

An adverse event or suspected adverse reaction is considered "serious" if, in the view of either the investigator or sponsor, it results in any of the following outcomes: Death, a life-threatening adverse event, inpatient hospitalization or prolongation of existing hospitalization, a persistent or significant incapacity or substantial disruption of the ability to conduct normal life functions, or a congenital anomaly/birth defect. Important medical events that may not result in death, be life-threatening, or require hospitalization may be considered serious when, based upon appropriate medical judgment, they may jeopardize the patient or subject and may require medical or surgical intervention to prevent one of the outcomes listed in this definition. Examples of such medical events include allergic bronchospasm requiring intensive treatment in an emergency room or at home, blood dyscrasias or convulsions that do not result in inpatient hospitalization, or the development of drug dependency or drug abuse.

- **Suspected adverse reaction**

Any adverse event for which there is a reasonable possibility that the drug caused the adverse event. For the purposes of IND safety reporting, "reasonable possibility" means there is evidence to suggest a causal relationship between the drug and the adverse event. Suspected adverse reaction implies a lesser degree of certainty about causality than adverse reaction, which means any adverse event caused by a drug.

- **Unexpected adverse event or unexpected suspected adverse reaction**

An adverse event or suspected adverse reaction is considered "unexpected" if it is not listed in the investigator brochure or is not listed at the specificity or severity that has been observed; or, if

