7.2.3. Reporting Adverse Events

- **Routine adverse events**

Adverse events that do not meet serious criteria (section 8.4) are considered routine adverse events. Routine adverse events are reported utilizing the appropriate eCRF page in the study database.

The investigator is reminded to comply with all institutional and local requirements as well as the requirements put forth by the IRB of record regarding reporting of routine adverse events.

- **Serious adverse events**

Any adverse event meeting serious criteria (section 8.2) occurring within the collection window must be reported following the instructions in Appendix 1 – Serious Adverse Event Reporting. **The timeframe for reporting** the event to the sponsor/CRO is **1 business day** of the clinical investigator becoming aware of the initial event or clinically significant follow-up information.

The Investigator must provide a causality assessment and must sign and date all SAE Report Forms.

If supporting documentation is included in the submission (e.g., hospital reports, consultant reports, death certificates, autopsy reports, etc.), all protected health information must be redacted. When appropriate, additional written reports and supporting documentation will be provided by the site for further clarification and information.

The investigator is reminded to comply with all institutional and local requirements as well as the requirements put forth by the IRB of record regarding serious adverse events.

- **Adverse events leading to study discontinuation**

Participants who have withdrawn, or were withdrawn, from the study due to an adverse event (regardless of attribution) will be followed by the investigator until resolution or a new baseline, provided the participant consents to being followed.

- **Attribution to Investigational Medical Product and Study Procedure**

The relationship of [⁶⁸Ga]FAPI-46 and the PET scan procedure to an adverse event will be assessed by the Investigator utilizing the FDA's December 2012 guidance *Safety Reporting Requirements for INDs and BA/BE Studies*.

The investigator must note if there is a reasonable possibility there is evidence to suggest a causal relationship between [⁶⁸Ga]FAPI-46 and the adverse event and if there is evidence to suggest a causal relationship between the PET scan procedure and the adverse event.

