7.2.4. Documentation

Case Histories / Participant Binders

Adverse events should be recorded within the participant's case book / study binder compliant

with ALCOA. At minimum, information captured must include:

- Term, harmonized to CTCAE v. 5. Do not use a verbatim term or medical jargon – for example, use “white blood cell decreased,” instead of *leukopenia* and “neutrophil count decreased,” rather than *neutropenia*.
- Severity grade (as per CTCAE v. 5)
- Date, onset
- Date, end
- Outcome (e.g., without sequelae, with sequelae, ongoing)
- Attribution to study drug (unrelated, probable, definite)
- Attribution to the study procedure (i.e., PET/CT scan) (unrelated, probable, definite)

Attributions must be confirmed by the study’s clinical investigator and documented by signature and date.

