8.2. Safety Analysis

All patients who receive any amount of [⁶⁸Ga]FAPI-46 will be included in the final summaries and listings of safety data.

Frequencies of patients experiencing at least one AE will be displayed by body system and preferred term according to MedDRA terminology. Detailed information collected for each AE will include: description of the event, duration, whether the AE was serious, intensity, relationship to study drug, action taken, clinical outcome, and whether or not it was a DLT. Intensity (severity) of the AEs will be graded according to the CTCAE v4.0. Emphasis in the analysis will be placed on AEs classified as dose limiting.

Summary tables will present the number of patients observed with AEs and corresponding percentages. The denominator used to calculate incidence percentages consists of patients receiving at least one dose of study medication. Within each table, the AEs will be categorized by MedDRA body system and preferred term. Additional subcategories will be based on event intensity and relationship to study drug.

Deaths and other SAEs will be tabulated.

Vital signs will be summarized using descriptive statistics.

Summary tables will be prepared to examine the distribution of laboratory measures over time.

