9.4 Imputation and Handling of Partial Dates

Patients with missing or invalid histopathology data (the standard of truth) will be considered positive for the primary region of interest, in line with the study design, which requires all

patients to be positive for PDAC in order to be eligible for inclusion. Missing SUV values for the primary tumor, where the response in the EDC is interpretable (i.e., ‘Yes’ to the eCRF question: ‘Is the image of technical quality for interpretation?’), will be treated as a region considered negative by the blinded reader. Otherwise, no imputation for missing data will be performed unless explicitly specified. Rules for partial and missing dates for AEs and medications are given in the [Appendices](#).

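### Leaving patients with a missing grade or relationship out of the SAP's grade and relatedness tables may under-count study drug-related TEAEs

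*SAP*

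**What the plan says.** **Missing grade or relationship.** SAP 10.7.1 applies its rule to "Patients who have reported TEAEs that are missing CTCAE toxicity grade or relationship to study drug". It states that patients with TEAEs "missing CTCAE toxicity grade or relationship to study drug will not be summarized in the tables by toxicity grade or relatedness", but "they will be included in the listings of AEs and tables not summarized by toxicity grade or relatedness". SAP 9.4 adds that, apart from the cases it names, "no imputation for missing data will be performed unless explicitly specified". Relationship to study drug is not among those cases.

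**Where the count is used.** SAP 5.2 (Table 2) lists study drug-related TEAEs among the summary measures of the safety estimand. SAP 10.7.1 plans them in the overview table and by SOC and PT.

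**Causality.** Protocol 7.2.2 defines a suspected adverse reaction as "Any adverse event for which there is a reasonable possibility that the drug caused the adverse event". Protocol 7.2.3 instructs: "The investigator must note if there is a reasonable possibility there is evidence to suggest a causal relationship between" the drug and the event. For the case history, Protocol 7.2.4 gives three levels: "Attribution to study drug (unrelated, probable, definite"). SAP 10.7.1 refers to Protocol 7.2 for attribution and takes the table data from the adverse event eCRF. It does not say which answers make an event study drug-related.

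**The concern.** In a relatedness table, leaving out an event of unknown relationship has the same effect on the numerator as calling it unrelated. The SAP takes the cautious side elsewhere: in Table 6 of its Appendix 2, an AE with a wholly missing start date is taken to be treatment-emergent. Unknown timing therefore defaults towards counting the event, while unknown causality defaults towards not counting it, and no reason is given.

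The rule is also written for patients, not events, and it joins two kinds of missing item to two kinds of table with the word or. Programmers could implement it in different ways and get different counts.

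Safety is a secondary objective. Few related events should be expected, since Protocol 4.4 cites more than 200 scans without a reported adverse event. With counts that small, one patient can decide whether the table shows no related event or one.

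**Working it through.** The documents give no expected rate of related TEAEs and no expected rate of missing relationships, so there is no figure of the plan's own to reproduce. The effect can be bounded per patient.

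**Inputs**
- N = 60, the planned maximum (SAP 6.1). Protocol 8.2 sets the incidence denominator as patients who received at least one dose. I assume that the SAP tables use it and that all 60 are dosed.
- r = patients with at least one TEAE recorded as related. Not given; assumed 0 or 3.
- m = patients whose only candidate related TEAE has no recorded relationship. Not given; assumed 0 to 6.
- d = patients with a TEAE recorded as related and another TEAE lacking grade or relationship. Not given; assumed 1.

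**Step 1: rule applied event by event.** The table shows r/N. Counting missing as related gives (r + m)/N. The difference is m/N, or 1/60 = 1.7 percentage points per patient. This is an upper bound on the under-count, because an event of unknown relationship need not be related.

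| r | m | Current rule, r/60 | Missing counted as related, (r + m)/60 |
|---|---|---|---|
| 0 | 0 | 0.0% | 0.0% |
| 0 | 1 | 0.0% | 1.7% |
| 0 | 3 | 0.0% | 5.0% |
| 0 | 6 | 0.0% | 10.0% |
| 3 | 0 | 5.0% | 5.0% |
| 3 | 1 | 5.0% | 6.7% |
| 3 | 3 | 5.0% | 10.0% |
| 3 | 6 | 5.0% | 15.0% |

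**Step 2: rule applied to the patient, as written.** The table shows (r − d)/N. With r = 3 and d = 1 this is 2/60 = 3.3%, although 3/60 = 5.0% have a TEAE recorded as related. Here the lost event was assessed as related, so the loss does not depend on guessing an unknown. It can arise from a missing grade alone.

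**Step 3: denominators.** The tables are also presented by cohort. Cohort sizes are not fixed in the documents. Each cohort column has a smaller denominator than the total, so one patient weighs more than 1.7 points there.

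**Step 4: the causality scale.** Protocol 7.2.2 and 7.2.3 ask whether causation is reasonably possible. The three levels in 7.2.4 have no place for an event judged possible but not probable. If the investigator records it as unrelated, the related count falls; if as probable, it does not. The direction cannot be determined from the text. Since the SAP does not define the related category and the eCRF answers are not shown, the size cannot be computed either.

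**The case against.** The strongest reply is that the rule will seldom operate. Protocol 8.2 names "relationship to study drug, action taken, clinical outcome" among the details collected for each AE. Protocol 7.2.4 makes attribution part of the minimum record, to be signed and dated by the investigator, and 7.2.3 makes a causality assessment mandatory for SAEs. The SAP also hides nothing: the listings and the overall, serious and fatal TEAE tables keep these events, and with at most 60 patients a reader can find an unattributed one. All of this stands, and it limits the size of the point. It does not explain why the default should favour the product, nor does it repair the patient-level wording.

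A reader might infer more than the documents support:
- **That related TEAEs will be under-counted.** This needs missing data, and the documents do not show that any exist.
- **That a relative loss can be quoted.** Three recorded related events and one unknown would suggest that a quarter are missed, but both counts are assumed and the unknown event is presumed related.
- **That the three-level scale also pushes the count down.** Its direction is open. It is a case-history minimum, whereas the tables come from an eCRF whose answer options are not in the documents. Protocol 7.2.3 separately requires the reasonable-possibility judgement, so it may be recorded elsewhere.

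It can also be said that a row for missing relationship would be as transparent as counting it as related, without assigning a causality nobody assessed. That is a fair alternative. Counting as related is a common conservative convention and matches the SAP's own treatment of missing start dates.

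**Conclusion.** The point holds as a minor one about reporting. Under SAP 10.7.1, study drug-related TEAEs may be under-counted if any relationship is missing, by up to 1.7 percentage points per affected patient at N = 60. Under the literal reading, a patient with a known related TEAE is also lost when another TEAE lacks a grade or relationship. With complete data both effects are zero. The number of affected patients cannot be known from the documents, and the percentages assume that all 60 patients are in the denominator.

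The effect is confined to the grade and relatedness tables. The listings, the overall TEAE tables and the primary sensitivity analysis are untouched. The mismatch between Protocol 7.2.4 and Protocol 7.2.2 and 7.2.3 is real, but it is an ambiguity to be reconciled, not a demonstrated bias.

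**What to change.** In SAP 10.7.1:
1. State the rule for events, so that a patient's complete events are always counted whatever is missing from that patient's other events.
2. Count a TEAE with missing relationship as study drug-related, and footnote the number so imputed.
3. Show missing grade as its own row instead of leaving the patient out.
4. State which eCRF answers count as study drug-related.

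Separately, reconcile the case-history scale in Protocol 7.2.4 with the reasonable-possibility standard in 7.2.2 and 7.2.3.

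The SAP items cost a few sentences and a default in the adverse event table program. They change no count if the data are complete; otherwise the reported related-event rate may be slightly higher. The scale is a protocol and data-collection matter. The SAP describes study conduct in the past tense, so the data may already have been collected, and an SAP edit cannot supply a judgement that was never recorded. In that case item 4 is what can still be settled.
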